1.0 BACKGROUND AND RATIONALE

Colorectal cancer is the 2nd leading cause of cancer related deaths in the US(1). Colon cancer accounts for 71% and rectal cancer for the remaining 29%(2). Treatment for both entities is primarily surgical with a 90% survival at 5 years when diagnosed in a localized stage, 70% for regional and 10% for metastatic disease(3). Imaging plays a crucial role in the diagnostic workup of these diseases. Both, CT and MR, have their roles in diagnosis and initial staging of both colon (CT colonography) and rectal cancer (Pelvic MR). Furthermore they also contribute substantially in follow up and restaging, along with PET-CT.

Determining T and N staging of rectal cancer is mainly done with MR given its superior tissue resolution over CT and PET-CT(4, 5). In particular for T staging similar accuracy was reported when comparing endoscopic ultrasound and MRI in cases of histologically proven rectal cancer (4). While T2 weighted sequences give a detailed anatomy and reach of the lesion as well as morphologic data regarding lymph nodes of the area, DWI sequences helps evaluate the cellular composition of both the tumor and lymph nodes showing as hyperintense lesions those with a high cellular component. On the other hand, PET-CT is used mainly in aggressive, or high grade, rectal cancer and locally advanced stages because of its high sensitivity depicting metastatic disease which might either change the therapeutic approach or suspend unnecessary interventions(6, 7). The diagnostic accuracy of PET/CT for M staging is higher than that of CT alone.

Follow up in successfully treated patients, both in colon and rectal cancer, contributes to increased survival rates, as it has been proven that patients undergoing liver imaging during follow up have a 25% lower mortality rate(8). While CT is the image modality of choice, because of availability and price, MR is more sensitive for detecting and classifying liver lesions(9) while PET-CT is more sensitive in detecting extrahepatic disease(10).

Given the obvious advantages, described above, of both MR and PET-CT in staging, follow up and restaging of these diseases, it is our objective to test the performance of PET-MRI in these diseases since it is our belief that this hybrid imaging modality will prove superior to current single imaging modality options, namely MRI, CT and PET-CT.

2.0 OBJECTIVES

Our objective is to test the diagnostic performance of PET-MRI in two different settings. The first setting is the staging of preoperative high-grade rectal cancer patients, defined by T3 stage or higher or N1 stage or higher or presence of metastasis, that are referred to PET-CT and MRI. In this population Pathology will be the gold standard when available for local staging and PET/CT for M staging. When Pathology is not available, both MRI and PET/CT results will be used to determine T and N stage.

The second setting is the follow up of colorectal cancer patients that are referred to PET-CT with or without a diagnostic MRI request by their physicians. In this second group the gold standard for recurrence will be obtained from analyzing CEA levels and PET/CT and MRI results. Pathology results will be used as well whenever available.

A secondary objective is to test different attenuation correction MR sequences and novel diagnostic MR sequences.

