3.0 PATIENT/SAMPLE SELECTION

Every patient that is scheduled to get a PET-CT at UH Case Medical Center either for preoperative high-grade rectal cancer or for colorectal cancer follow-up will be invited to join this pilot study. Initially, 10 patients per group will be invited to participate. We expect to recruit this number of patients in a two year period at the most.

Inclusion Criteria:

- Either having a T3 (The cancer has grown through the muscularis propria and into the outermost layers of the colon or rectum but not through them) or higher, node positivity or metastatic lesion in the context of rectal cancer or being studied for colorectal cancer follow up, independent of the renal function
- PET-CT should be requested by a referring physician. In the case of having an MR requested as well, it will be reported from the MRI images generated in the PET-MRI
- Stable physical medical conditions to undergo a MRI

- Informed consent must be given and signed prior to study enrollment
- Patient should be over 21 years old

Exclusion Criteria

- Refuse to give and/or sign the informed consent
- Subjects who do not meet the above mentioned inclusion criteria
- Subjects who have a pacemaker
- Subjects who have a metallic prostheses either in the pelvis or in the abdomen that will interfere with the MR imaging of that anatomical area
- Subjects who suffer from claustrophobia
- Pregnant women
- Cognitive impairment that affects the subjects ability to give consent

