8.0 STATISTICAL CONSIDERATIONS

The sample size was determined by the number of patients Philips Healthcare® has agreed to fund and is acceptable for a pilot study. Continuous variables will be expressed as mean \pm standard deviation. Comparisons between continuous variables will be performed by using the Student *t* test. Comparisons between qualitative variables will be performed by using the χ^2 test with the Yates' correction or McNemar's test as appropriate.

Sensitivity, specificity, positive and negative predictive values, and accuracy for PET-CT and PET-MRI with their 95% confidence interval will be calculated by using the standard formulas according to the criterion standard. Concordance between PET-CT and PET-MRI techniques will be assessed by using the McNemar test that evaluates whether the discrepancies between both techniques are higher than those observed by chance alone.

All calculations and statistical parameters will be calculated using Systat, Ver. 13.05 (Systat Software, Chicago, IL) or MedCalc Software, Ver. 12.3 (MedCalc Software bvba, Brussels, Belgium).

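### The staging group is selected on advanced stage, yet Section 8.0 offers only binary accuracy measures with no target or cut-point; if T3+ is the target, specificity and NPV are likely to be near-uninformative

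*Combined protocol and SAP*

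**What the plan says.** Section 2.0 sets out to test PET-MRI for staging preoperative high-grade rectal cancer, "defined by T3 stage or higher or N1 stage or higher or presence of metastasis". Section 3.0 repeats the three routes as an inclusion criterion: T3 "or higher, node positivity or metastatic lesion in the context of rectal cancer". Neither section says which examination establishes the stage at entry.

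On size, Section 3.0 says "Initially, 10 patients per group will be invited to participate". Section 8.0 explains that the number is what the funder "has agreed to fund and is acceptable for a pilot study". No precision target or expected stage distribution is given.

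On the reference standard, Section 2.0 says "Pathology will be the gold standard when available for local staging and PET/CT for M staging", and then "When Pathology is not available, both MRI and PET/CT results will be used to determine T and N stage".

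On analysis, Section 8.0 says: "Sensitivity, specificity, positive and negative predictive values, and accuracy for PET-CT and PET-MRI with their 95% confidence interval will be calculated". The comparison is with the criterion standard. The section does not say which condition counts as positive, at what cut-point, or on what unit of analysis. It gives no measure designed for an ordered stage.

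**The concern.** Specificity needs patients who do not have the condition. The first entry route is T3 or higher. If T3+ is also the condition to be detected, the negatives can only be T1-2 patients who came in through nodes or metastasis, plus patients whose entry stage differs from their reference stage. If the condition is high-grade disease as a whole, every patient is positive at entry, and only a disagreement between entry and reference stage can produce a negative.

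Sensitivity, PPV and accuracy are then dominated by patients who are positive almost by selection. They could look good for a scan that cannot tell T3 from T2. A pilot reported that way could give a misleading picture of staging performance, although the data needed for a more informative summary will already have been collected.

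**Working it through.** **Inputs.** n = 10 in the staging group (Section 3.0). The entry rule has three routes joined by *or* (Sections 2.0 and 3.0). The share q of enrolled patients whose reference stage is below T3 is not in the documents. I assume 5% to 30% and also look at 40% and 50%. The sample size was set by funding, so there is no calculation in the plan to reproduce.

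**Step 1: number of reference-negatives for T3+ against T1-2.** Expected number = 10q. P(none) = (1 − q)^10. P(3 or fewer) is the binomial sum.

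| Assumed q | Expected below T3 | P(none) | P(3 or fewer) |
|---|---|---|---|
| 5% | 0.5 | 0.95^10 = 0.60 | 0.999 |
| 10% | 1 | 0.90^10 = 0.35 | 0.99 |
| 20% | 2 | 0.80^10 = 0.11 | 0.88 |
| 30% | 3 | 0.70^10 = 0.03 | 0.65 |
| 40% | 4 | 0.60^10 = 0.006 | 0.38 |
| 50% | 5 | 0.50^10 = 0.001 | 0.17 |

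**Step 2: precision of specificity at its best.** If all m negatives are read correctly, the exact (Clopper-Pearson) 95% lower limit is 0.025^(1/m), and the upper limit is 100%.

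- m = 1: 2.5%
- m = 2: 15.8%
- m = 3: 29.2%
- m = 5: 47.8%
- m = 0: specificity is undefined

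Any patient left out for lack of pathology reduces m further.

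**Step 3: NPV.** Its denominator is test-negatives, not patients below T3. With d patients below T3, expected test-negatives = d × specificity + (10 − d) × (1 − sensitivity). Assume d from 0 to 3, and sensitivity and specificity each from 0.7 to 0.9.

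- Smallest: d = 0, sensitivity 0.9, giving 10 × 0.1 = 1.0.
- Largest: d = 3, specificity 0.9, sensitivity 0.7, giving 3 × 0.9 + 7 × 0.3 = 4.8.

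So NPV would rest on about 1 to 5 patients. With d = 0, any NPV that can be calculated is 0.

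**Step 4: a scan with no discrimination.** Suppose every patient is called T3+. Sensitivity is 100%. PPV and accuracy both equal 1 − q, which is 95% at q = 5% and 70% at q = 30%.

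**The case against.** The arithmetic is not in dispute. The objections concern how far it reaches.

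- *Section 8.0 never names T stage.* This is correct. A reader might infer that the plan promises specificity and NPV for T3+, or that it forces a cut at the entry threshold. It does neither. N+, M1, recurrence in the follow-up group, or T4 against T3 would also fit the text, and accuracy could be read as the proportion correctly staged. The T3+ analysis is therefore a conditional case. But staging is this group's objective, and leaving the target open is itself a gap.
- *The count of negatives is assumed.* This also stands. A reader might take zero to three as a property of the design. The entry rule allows 0 to 10, because T1-2 patients with nodal or metastatic disease qualify and entry stage may differ from reference stage. At q = 30%, the chance of more than 3 is 35%. Even so, 5 negatives all read correctly leave a lower limit of only 48%.
- *Specificity can be estimated.* True, unless there are no negatives. To say that it cannot be estimated would be too strong; very imprecise is the accurate description. NPV also has a different denominator and needs its own statement.
- *N and M are entry routes too.* This stands. It would be inconsistent to restrict T3+ specificity and leave N and M untouched. For M there is a further problem: PET/CT is the reference, so its own sensitivity and specificity are 100% by definition.
- *It is a pilot, and wide intervals show their own imprecision.* This excuses small numbers and rules out any claim of a failed power target. It does not justify relying on binary measures that the entry rule undermines when a better summary costs nothing to collect. The better summary is imprecise too: 8 of 10 correctly staged has an exact interval of 44% to 97.5%. It does, however, use every patient with a reference stage and keep the ordering.

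**Conclusion.** The point holds in conditional form. Entry on T3+, N1+ or metastasis with about 10 patients, combined with undefined binary measures, means that a T3+ against T1-2 analysis would probably have few reference-negatives: 0.5 to 3 expected, with a 60% to 3% chance of none, at an assumed 5% to 30% below T3. Specificity would be undefined or have a lower limit no better than 29% on three or fewer patients. NPV would rest on about 1 to 5 test-negatives under the assumed sensitivity and specificity of 0.7 to 0.9. Sensitivity, PPV and accuracy could be high without any discrimination.

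The stage mix and reading accuracy are my assumptions. What the documents establish is the entry rule, the planned number, the list of measures and the missing target. They do not establish that these quantities are inestimable by design. This is an inexpensive improvement that should be made, not a fatal flaw.

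**What to change.** In Section 8.0, for the staging group:

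1. Make the T and N measures the proportion correctly staged and the counts over- and understaged, as n/N with exact 95% intervals. Show patients with pathology separately from those on the imaging fallback. In the fallback group the reference is itself imaging, and Section 5.1 has a requested MRI reported from the PET-MRI images, so agreement there is not independent evidence. Weighted kappa may be added as description only; it will be unstable at this size.
2. For any binary measure kept, name the target condition and the cut-point.
3. Report T3+ specificity and NPV only as n/N with exact intervals, stating that they are not reliably estimable under the entry rule.
4. For N+ against N0 and M1 against M0, report n/N with exact intervals and the same selection caveat. Do not report PET-CT's own accuracy for M stage, where PET/CT is the reference.

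The cost is a change of statistical wording. It needs no further patients, scans or data. The downside is that T-stage specificity and NPV are no longer headline results, and splitting by reference type makes each denominator smaller.

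### M stage: with PET/CT as the reference, PET-CT's accuracy figures would be circular and PET-MRI's would measure only agreement with PET-CT

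*Combined protocol and SAP*

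**What the plan says.** Section 2 (Objectives) sets the references for the staging group: "In this population Pathology will be the gold standard when available for local staging and PET/CT for M staging". The next sentence is a fallback for local staging only: "When Pathology is not available, both MRI and PET/CT results will be used to determine T and N stage". No biopsy, follow-up or other independent reference is named for M stage in this group. The sentence "Pathology results will be used as well whenever available" belongs to the follow-up group, whose reference is described as: "In this second group the gold standard for recurrence will be obtained from analyzing CEA levels and PET/CT and MRI results".

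Section 8 (Statistical Considerations) lists what is calculated: "Sensitivity, specificity, positive and negative predictive values, and accuracy for PET-CT and PET-MRI with their 95% confidence interval", and says that these "will be calculated by using the standard formulas according to the criterion standard". It names no endpoint and exempts none. The only criterion standards in the documents are the gold standards of Section 2. Section 8 adds: "Concordance between PET-CT and PET-MRI techniques will be assessed by using the McNemar test", a test it describes as one that "evaluates whether the discrepancies between both techniques are higher than those observed by chance alone".

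Section 5.1 describes one PET-CT per patient, the clinically requested one, with the PET-MRI done directly before or after it on the same tracer injection. Section 3 plans 10 patients per group.

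**The concern.** Read together, Sections 2 and 8 make PET-CT both a test under evaluation and the truth it is evaluated against. A scan compared with its own reading has no false positives and no false negatives, so its result is known before any patient is scanned.

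The consequence for PET-MRI matters more. Section 1 expects PET-MRI to prove superior to PET-CT, and notes that MR is the more sensitive modality for liver lesions. It supports PET/CT for M staging as more accurate than CT alone, not as equivalent to truth. Yet a real liver metastasis seen on PET-MRI and missed on PET-CT would be tabulated as a PET-MRI false positive. A metastasis missed by both would be tabulated as a correct negative for both. On M stage PET-MRI could at best equal PET-CT.

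**Working it through.** The plan states no accuracy, power or significance figure, so there is nothing to reproduce first.

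**Inputs from the documents.** M-stage reference: PET/CT (Section 2). Tests scored: PET-CT and PET-MRI (Section 8). One PET-CT per patient (Section 5.1). Ten patients in the group (Section 3).

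**Assumed inputs.** The documents give neither the proportion with metastases nor PET-CT's true accuracy. I take 30% with metastases (range 20% to 50%) and PET-CT sensitivity/specificity of 95/98, 80/95 and 70/90.

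**Step 1. PET-CT against itself.** If PET-CT is positive in m of 10 patients, then TP = m, FP = FN = 0 and TN = 10 − m. Sensitivity and PPV are m/m, specificity and NPV are (10 − m)/(10 − m), and accuracy is 10/10. Every defined measure is 100% for any m from 0 to 10. At m = 0 sensitivity and PPV are 0/0; at m = 10 specificity and NPV are 0/0. The exact 95% lower limit for 10/10 is 0.025^(1/10) = 69.2%, an interval around a quantity that is fixed by identity.

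**Step 2. One concrete table.** Suppose 3 of 10 patients truly have metastases, PET-CT finds 2 of them with no false positives, and PET-MRI is right in all 10. Against PET/CT, PET-MRI scores sensitivity 2/2, specificity 7/8 = 87.5%, PPV 2/3 = 66.7% and accuracy 9/10 = 90%. PET-CT, which missed a metastasis, scores 100%.

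**Step 3. Expected size for a perfect PET-MRI.** With PET/CT taken as truth, reported sensitivity = P(both positive)/P(PET-CT positive), specificity = P(both negative)/P(PET-CT negative), and accuracy = P(the scans agree). For a perfect PET-MRI at 30% prevalence, accuracy = 0.3·Se + 0.7·Sp of PET-CT, and the chance of at least one discordance in 10 patients is 1 − accuracy^10.

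| PET-CT true Se/Sp | Reported PET-MRI Se | Reported PET-MRI Sp | Reported PET-MRI accuracy | At least one discordance in 10 |
|---|---|---|---|---|
| 95/98 | 0.285/0.299 = 95.3% | 0.686/0.701 = 97.9% | 97.1% | 25% |
| 80/95 | 0.240/0.275 = 87.3% | 0.665/0.725 = 91.7% | 90.5% | 63% |
| 70/90 | 0.210/0.280 = 75.0% | 0.630/0.720 = 87.5% | 84.0% | 83% |

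Over 20% to 50% prevalence as well, reported accuracy runs from 97.4% (0.2 × 0.95 + 0.8 × 0.98) to 80.0% (0.5 × 0.70 + 0.5 × 0.90), and the chance of any discordance from 23% to 89%.

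**Step 4. The error can go either way.** Let both scans have 80/95 at 30% prevalence, so true accuracy is 0.3 × 0.80 + 0.7 × 0.95 = 90.5%. With independent errors, PET-MRI is reported at 0.3(0.64 + 0.04) + 0.7(0.9025 + 0.0025) = 83.8%. With fully overlapping errors it is reported at 100%.

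**Step 5. McNemar.** The test uses only the discordant pairs and asks whether they fall more one way than the other. Three discordances each way in 10 patients give exact p = 1.0 with agreement of only 4/10. A non-significant result is therefore not evidence of concordance.

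**The case against.** **Section 8 does not name M stage.** The stated objective is the performance of PET-MRI, Section 6 gives the PET-MRI data as the study parameter, and a PET-CT accuracy row has real meaning for T and N against pathology. A reader might infer that the plan certainly produces a 100% PET-CT result for M stage. The documents do not go that far: the figure requires that M stage is tabulated for PET-CT and that one reading serves as both test and reference. But Section 8 exempts nothing, and the PET-MRI half of the problem remains even if the PET-CT row is never produced.

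**A second reading may be intended.** Sections 5.1 and 9 separate clinical from research archives, and Section 5.1 foresees research review turning up findings not seen clinically. No separate PET-CT research reading is stated. If there were one, 100% would no longer be automatic, but the figures would measure repeatability between readings, not accuracy.

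**The agreement figure is already there.** This is correct. PET-MRI's accuracy against PET/CT is numerically the percent agreement, and its two-by-two table holds the discordant counts. The defect is in what the figures are called and in the PET-CT row, not in a missing calculation.

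**It is a small pilot without a formal hypothesis.** That excuses imprecision; it does not make a circular figure informative. The independence used for the low end in Step 4 is also doubtful for two scans sharing one tracer injection, which points toward the overlapping end. The perfect PET-MRI figures in Step 3 do not use that assumption.

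**Wider inferences.** A reader might conclude that every accuracy result is circular, or that accuracy must be restricted to patients with an independent reference. Neither follows. T and N against pathology are unaffected. The T/N fallback and the recurrence reference do include the scans being scored, since a requested MRI is reported from the PET-MRI images. But the rule for combining the sources is not stated, so the direction and size of any bias cannot be derived. Restriction would be a debatable trade: fewer patients out of 10, possible partial-verification bias, and possible reliance on CEA without tissue.

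**Conclusion.** The point holds for M stage in the staging group and should be corrected before any M-stage result is tabulated. On the plain reading of Sections 2 and 8, with the one PET-CT reading described, every defined PET-CT measure is 100% regardless of truth, and PET-MRI can never score higher. PET-MRI's M-stage figures measure agreement with PET-CT, may lie above or below its true accuracy, and cannot inform the superiority belief in Section 1. T and N against pathology still can.

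The circularity is a matter of definition and needs no assumed input. The sizes do: a perfect PET-MRI reported at 97.1% to 84.0% accuracy rests on an assumed 30% prevalence and assumed PET-CT performance of 95/98 to 70/90. For the T/N fallback and recurrence there is only a caveat, which I do not quantify.

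**What to change.** In Sections 2 and 8:

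- Do not report PET-CT accuracy for M stage against PET/CT, and do not label PET-MRI's M-stage figures as sensitivity, specificity, predictive values or accuracy.
- Report M stage as PET-CT versus PET-MRI agreement: overall percent agreement with an exact 95% confidence interval, and the number of discordant patients in each direction. With 10 patients the exact intervals are 69.2% to 100% for 10/10, 55.5% to 99.7% for 9/10 and 44.4% to 97.5% for 8/10.
- Describe McNemar as a test of asymmetry between the scans, not of how often they agree.
- As a caveat, report T/N results that rest on the imaging fallback, and recurrence results whose reference includes the scans, separately from those in pathology-verified patients, with the number in each.

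The cost is wording plus the relabelled agreement statistic; no new scans, visits or patients are needed. The downside is that M stage becomes an agreement result and cannot say which scan is right when they differ.

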5.0 RESEARCH PLAN

5.1 Study procedures and data analysis plan

Patients who enroll in this study will receive their clinically requested diagnostic PET-CT and a PET-MRI. When a diagnostic MRI is additionally requested, a report will be generated from the MRI images obtained in the PET-MRI. Both exams will be performed at the Seidman Cancer Center as part of their normal diagnostic care and will meet all of the institutionally imposed criteria for these studies. For research purposes, additional MR sequences that are completely harmless to the patient, but haven't yet been FDA approved for the clinical arena, will be performed. If any additional relevant information is discovered because of these latter sequences proper communication of these findings to the referring physician will be done.

Using the same F18-FDG injection PET-MRI will be performed, before or after the clinically requested PET-CT. If an MRI has also been requested, the report will be generated from the MRI images performed in the same scanner as the PET-MRI. After completion of the first scan, be it the PET-MRI or the PET-CT, the patient will immediately undergo the other examination. No additional F18-FDG injection will be required. MR contrast agents may be injected if it's requested by the referring physician and there are no contraindications. As a preparation for the MRI examination, all subjects except those with prior rectal surgery will receive a small amount of rectal gel to allow enhanced lesion detection. Intramuscular glucagon (1 mg) will be administered to all subjects to help relax the bowels during the MRI examination, unless there are contraindications to it which include history of glucagon hypersensitivity or pheochromocytoma. If the MRI is clinically ordered, the rectal gel and glucagon administrations are standard of care. However, they are research if the MRI is not ordered by the referring physician.

The patient will be inside the PET-MRI scanner for approximately 60-90 minutes whether or not an MRI is performed.

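### For staging patients without pathology, the T and N reference is built from PET-MRI's own MRI and from PET/CT, so their accuracy figures have no independent truth behind them

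*Combined protocol and SAP*

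**What the plan says.** Section 2.0 sets the preferred standard for the staging group: "Pathology will be the gold standard when available for local staging and PET/CT for M staging". It then adds the fallback: "When Pathology is not available, both MRI and PET/CT results will be used to determine T and N stage". It gives no rule for patients in whom MRI and PET/CT disagree, and no expected share with pathology.

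The MRI in that fallback is identified in two places. Section 3.0: "In the case of having an MR requested as well, it will be reported from the MRI images generated in the PET-MRI". Section 5.1: "When a diagnostic MRI is additionally requested, a report will be generated from the MRI images obtained in the PET-MRI". Section 5.1 also lists what each participant undergoes: "Patients who enroll in this study will receive their clinically requested diagnostic PET-CT and a PET-MRI". No stand-alone MRI appears.

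Section 1.0 gives the protocol's own view of which modality matters here: "Determining T and N staging of rectal cancer is mainly done with MR given its superior tissue resolution over CT and PET-CT".

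Section 8.0 calculates sensitivity, specificity, predictive values and accuracy, with 95% confidence intervals, for PET-CT and PET-MRI against the criterion standard. It does not distinguish patients by the source of that standard.

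**The concern.** A diagnostic accuracy figure means something only if the reference is independent of the test being scored. In a staging patient without pathology, the PET-MRI call on T and N and the reference call draw on the same MR images, and PET/CT supplies the rest of the reference. Each technique is marked partly against itself. The documents describe no independent MRI, blinded reading, adjudication panel or pathology-only analysis that would break this link.

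Local staging is where the rationale expects MR to contribute most, and Section 1.0 states the belief that PET-MRI will prove superior to existing options. If patients with and without pathology enter one accuracy figure, that figure depends partly on how many had a specimen and on how disagreements were settled. A larger sample would not remove the problem.

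**Working it through.** The plan has no figure of its own to reproduce: Section 8.0 sets the sample size by funding, and Section 3.0 gives 10 patients per group initially. The calculation below is an illustration, and every input is an assumption.

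**Inputs**
- a = 80%: true accuracy of PET-MRI, treated as a two-category T or N call, with the PET-MRI call taken to be its MRI call.
- b = 70%: true accuracy of PET/CT, with errors independent of MRI.
- f: share of staging patients without pathology.
- w: share of MRI–PET/CT disagreements that the fallback settles in favour of MRI.

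**Step 1. Agreement between the two techniques.** They agree when both are right or both are wrong: 0.80 × 0.70 + 0.20 × 0.30 = 0.62. They disagree in 0.38.

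**Step 2. Score against the fallback.** PET-MRI matches it in c = 0.62 + 0.38w of patients. PET-CT matches it in 1 − 0.38w.

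**Step 3. Apparent accuracy if all patients are combined.** PET-MRI: (1 − f) × 0.80 + f × c. PET-CT: (1 − f) × 0.70 + f × (1 − 0.38w). With f = 50%:

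| Fallback follows | c | PET-MRI (true 80%) | PET-CT (true 70%) | Difference (true 10 points) |
|---|---|---|---|---|
| MRI always (w = 1) | 100% | 90% | 66% | 24 |
| MRI in 80% | 92.4% | 86.2% | 69.8% | 16.4 |
| Each equally (w = 0.5) | 81% | 80.5% | 75.5% | 5 |
| PET/CT always (w = 0) | 62% | 71% | 85% | −14 |

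**Step 4. Where the sign changes.** Among fallback patients, PET-MRI is overstated when 0.62 + 0.38w > 0.80, that is, w above about 47%. Its advantage there is 0.76w − 0.38, which exceeds the true 0.10 only when w is above about 63%.

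**Step 5. Dependence on f.** With w = 1, PET-MRI's apparent accuracy is 0.80 + 0.20f: 85% at f = 25%, 90% at 50%, 95% at 75%. At f = 0 there is no bias.

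**Step 6. Dependence on independent errors.** If the two techniques tend to err in the same patients, agreement rises above 62%. At the extreme, where every MRI error is also a PET/CT error, it is 0.70 + 0.20 = 90%, and PET-MRI is overstated whatever w is. The documents give no basis for choosing between these cases.

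**Step 7. Precision with pathology only.** Exact (Clopper-Pearson) 95% intervals: 8 of 10 correct gives 44% to 97%; 4 of 5 correct gives 28% to 99%.

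**The case against.** Four arguments deserve an answer.

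*The direction is not fixed.* A reader might infer that PET-MRI's accuracy, and its lead over PET-CT, must be inflated. The documents do not support that. The fallback uses PET/CT as well as MRI, so the comparator is also part of its own reference, and no weighting is given. Under equal weighting the illustration leaves PET-MRI almost unchanged and shrinks its lead. Section 1.0 makes MR dominance likely, but it is general rationale, not a rule for settling disagreements. This objection stands, and it limits the claim.

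*Some patients might have PET/CT as the only reference.* This could be inferred because the inclusion list in Section 3.0 requires only a PET-CT request. But Section 2.0 defines the staging group as patients "that are referred to PET-CT and MRI", and the Section 3.0 list is shared with the follow-up group, where MRI is optional. The inference should not be drawn; at most the wording of the two sections could be aligned.

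*Combining the two kinds of patient is not stated.* True: Section 8.0 neither says nor excludes it. But it provides for no separation, and the fallback patients' figures lack independence even if shown alone.

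*This is a small pilot in preoperative patients, so few may lack pathology.* That is possible; the share is not given. Small size excuses wide intervals, not a reference that contains the test. With 10 patients, two or three without pathology are already 20% to 30% of the denominator.

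**Conclusion.** The point holds in a limited form. For staging patients without pathology, the T and N reference includes images from both techniques under comparison, and nothing elsewhere in the documents repairs this. Accuracy measures for those patients, or any total that includes them, cannot be read as accuracy against truth. Patients with pathology are unaffected.

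Inflation of PET-MRI's T and N accuracy is the likely direction, given the protocol's own statement about MR, but it is not demonstrated. With assumed true accuracy of 80% and half the patients without pathology, the independent-error illustration runs from 71% to 90%, depending on how the fallback is decided. The size for this trial cannot be computed, because the share without pathology, the weighting of MRI against PET/CT and the true accuracies are all unstated. The need for the change does not depend on the direction.

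**What to change.** In Section 2.0, state that T and N accuracy is assessed against pathology, and that in patients without a specimen the MRI and PET/CT findings are descriptive and not a gold standard.

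In Section 8.0, state that:
- the primary T and N sensitivity, specificity, predictive values and accuracy, for both PET-MRI and PET-CT, are calculated only in staging-group patients with a pathology specimen;
- patients without pathology are kept in a separate table showing the T and N category on each technique and the agreement between them, not labelled as accuracy;
- the numbers with and without pathology appear beside each figure.

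No scan, visit or procedure is added, and no patient leaves the study. There are two costs. Fewer patients contribute to the accuracy table, so intervals widen to the order shown in Step 7. Patients with pathology may also be a selected subset: entry admits metastatic disease, and Section 1.0 notes that PET-CT findings can alter or halt planned treatment, so imaging may influence who has a specimen. The plan should name this selective verification as a limitation.
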